### 2.4.2. Baseline Patients' Characteristics

The following parameters will be presented by treatment group on the ITT population as appropriate to draw up a recapitulation of the patients' characteristics at the time of enrolment.

If 2 Screening/Baseline visits are performed for a patient the latest Screening/Baseline data will be considered for analyses.

- Age, gender and pregnancy test (Done, Result);

## STATISTICAL ANALYSIS PLAN

REDUCE\_FMR - SAP\_V2  
2018\_08\_06\_CT

REDUCE FMR Trial

Page 16/22

- Medical history (General: History of COPD and History of diabetes, Cardiovascular: History of hypertension, History of hyperlipidemia requiring medication, History of angina pectoris, History of myocardial infarction, History of heart failure, History of arrhythmias, History of ICD implant, History of permanent pacemaker implant, History of coronary artery disease, History of cardiovascular surgical intervention, if subject not treated with the CARILLON implant, which other heart failure therapy is the patient eligible for ?, History of cerebral vascular disease).
- Physical exam (Cardiovascular, Peripheral vascular, Pulmonary, Neurological, Allergies and Other), Vital signs (Height (cm), Weight (kg), BMI (kg/m^2), Resp (rr), SpO2 (%), Temperature (°C), Systolic and Diastolic blood pressures (mmHg)),
- NYHA class
- ECG (12- Lead) (Done)
- Six minute walk test (Total distance walked (meters),
- Transthoracic Echo (TTE) (Heart rate (bpm), Systolic and Diastolic blood pressures (mmHg), MR Grade, LVEF (%), LVEDD (mm) or LVEDD/BSA (cm/ m^2))
- Exercise TTE results (Resting: Heart rate (bpm), Systolic and Diastolic blood pressures (mmHg), Symptoms and Intensity, Test conclusion: Work load (Watts), Heart rate (bpm), Systolic and Diastolic blood pressures (mmHg), Symptoms and Intensity)
- Transesophageal Echo (TEE) (Done);
- Hematology tests (Hemoglobin, Hematocrit, WBC, Platelets and other CBC results abnormal if any)
- Chemistries (Sodium, Potassium, Chloride, BUN, Creatinine or eGFR, Glucose, NT-BNP and other chemistry results abnormal if any)
- Pre-Procedure Chemistries (Creatinine or eGFR, Cardiac Troponin cT and other chemistry results if any)
- Pre-procedure Coagulation tests (Prothrombin Time (PT) and Partial Thromboplastin Time (PTT))
- Quality of life (KCCQ, SF-12).

Those baseline parameters will be compared in order to identify any imbalance following randomization using the Student (or Wilcoxon) test or Chi (or Fisher) test as appropriate.

### 2.4.1. Procedure Characteristics

#### 2.4.1.1. Pre-procedure

The following parameters will be presented by treatment group on the ITT population as appropriate to draw up a recapitulation of the pre-procedure characteristics.

- Type of sedation;
- Access site;
- Coronary Angiography: (Prior to implant RCA and LCX TIMI flows);
- Pre-implant pressures (LVEDP (mmHg), PAP (mmHg), Mean PAP (mmHg), PCWP (mmHg) and Mean PCWP (mmHg)),

The above parameters will be compared in order to identify any imbalance following randomization using the Student (or Wilcoxon) test or Chi (or Fisher) test as appropriate

The following parameters will be descriptively presented based on attempts number instead of patients number:

- CS/GCV length (CS Ostium to GCV/AIV Junction)
- Presence of Coronary stent in implant zone;
- Average Great Cardiac Vein (GCV) diameter (mm)
- Average Coronary Sinus (CS) diameter (mm).

#### 2.4.1.2. *Device implant*

The following parameters will be presented by population as appropriate to draw up a recapitulation of the CARILLON device implant characteristics:

- Number of attempts;

The following parameters will be presented based on CARILLON implant attempts number instead of patients number:

- CARILLON Implant size selection (Distal anchor size (mm), Proximal anchor size (mm), implant length (mm));
- Actual distal anchor location from CS ostium (cm), Actual proximal anchor location from CS Ostium (cm) and Proximal anchor displacement (prior decoupling);
- Post-implant pressures (LVEDP (mmHg), PAP (mmHg), Mean PAP (mmHg), PCWP (mmHg) and Mean PCWP (mmHg));
- Coronary Angiography (After proximal anchor locked Post-implant RCA and LCX TIMI flows (mm));
- Device successfully decoupled;

#### 2.4.1.3. *Procedure conclusion*

The following parameters will be presented by treatment group on the ITT population as appropriate to draw up a recapitulation of the post-procedure characteristics.

They will be compared using the Student (or Wilcoxon) test or Chi (or Fisher) test as appropriate.

- Procedure duration;
- Post implant Cine imaging protocol executed
- Equipment used to collect cine imaging
- Presence of change to coronary artery flow;
- Implant relationship to coronary artery;
- Number of arteries crossed;
- Total time of fluoroscopy (minutes), total heparin used (units), total contrast used (mL);

### 2.4.2. **Primary Endpoint**

The primary analysis will be performed on the Intent to treat (ITT) population.

The primary efficacy endpoint is to compare the change in regurgitant volume from baseline at 12 months between the treatment and control groups using a two-sided, two-sample t-test (or Wilcoxon Rank sum test as appropriate). The corresponding 95% confidence interval on the between-group difference will also be calculated and presented.

A sensitivity analysis of the primary efficacy endpoint analysis on the ITT population will be performed, using the last observation carried forward (LOCF) missing data imputation on the regurgitant volume at 12 months. The same comparison analysis as mentioned above for the primary efficacy endpoint will be performed.

Two other additional analyses will be performed on the primary efficacy endpoint on:

- As-treated population
- Per-protocol population

The same comparison analysis as for the primary efficacy endpoint mentioned above will be used

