The clinical relevance of this magnitude of a difference is supported by other trials evaluating the clinical impact of functional mitral regurgitation. For example, Amigoni showed in the VALIANT trial database that a 1% increase in FMR was associated with an increased risk of heart failure hospitalization, and an increased risk of death or heart failure hospitalization.³² Extending the clinical significance to mortality, Grigioni showed in a group of patients with Q-wave MI that those patients with a regurgitant volume >30 ml demonstrated higher mortality than those regurgitant volume <30 ml (RR 1.13 per 10 ml RVol increase).³³ In CRT candidate patients with at least mild MR and an average LVEF $25 \pm 7\%$, Madaric showed that CRT decreased the regurgitant volume from 36 ± 19 ml to 25 ± 11 ml, but he also showed that even an increase in regurgitant volume from 25 ± 11 ml at rest to 29 ± 12 ml with exercise was statistically significant to $p < 0.001$.³⁴ Lastly, Bursi noted in their study of heart failure after myocardial infarction that patients with MR had worse outcomes, which exhibited a graded ‘dose-response’ relationship with the severity of MR, a pattern that supports causality.³⁵ These data taken together suggest that a small change in FMR (e.g., 1%) can be clinically significant, and the 10 ml difference between populations proposed in this study is similar to the magnitude of change seen in other trials, and is clinically relevant.

Data Analysis

The mean improvement in regurgitant volume for each treatment group, from baseline to twelve months, will be compared in a two-sided, two-sample t-test. The 95% confidence interval on the between-group difference will also be calculated and presented. If assumptions of normality are violated, the nonparametric Mann-Whitney test will be used to assess statistical significance, and the 95% confidence interval on the

difference between groups will be calculated using the Hodges-Lehmann estimate and distribution-free confidence interval based on a Wilcoxon Rank Sum test. The primary analysis will be conducted on the intent-to-treat population, and supportive analyses will be performed on the previously defined per-protocol and as-treated populations (reference Section 6.2: Study Analyses). Further supportive analyses will be conducted which characterize the longitudinal effect of treatment on regurgitant volume in a repeated measures regression model.

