### 2.1.3. Inferential Analysis

Data will be compared between the two groups using bilateral tests at the type I error 5% level.

- *Continuous variables*: the appropriate test will be chosen depending on the data distribution.  
The normality of quantitative data will be tested using the Shapiro-Wilk test.
  - if the normality test pvalue is > 0.05, the data will be considered as normally distributed and the Student test will be used.
  - else, the data will be considered as not normally distributed and the Wilcoxon Rank Sum test will be used.
- *Categorical variables*: the appropriate test will be chosen depending on the expected cell frequencies:
  - If all expected cell frequencies are  $\geq 5$  then the Chi test will be used.
  - Otherwise, the Fisher's exact test will be used.

The 95% confidence interval in regurgitant volume mean difference from baseline to 12 months will be presented by treatment group. If assumptions of normality are violated, the 95% confidence interval will be calculated using the Hodges-Lehmann estimate and distribution-free confidence interval based on a Wilcoxon Rank Sum test.

Further supportive analyses will be conducted which characterize the longitudinal effect of treatment on regurgitant volume in a repeated measures regression model, using a mixed effects model approach. Fixed effects will be treatment group and time effect. Site effect will be a random effect. Interaction between treatment group and site will also be studied.

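### The primary test on change does not adjust for baseline regurgitant volume, and a normality pre-test can move the test and interval off the stated mean difference

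*SAP*

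**What the plan says.** Protocol 6.6 and SAP 2.2 define the parameter as the mean change in regurgitant volume from baseline to 12 months, and both hypotheses are about means. In Protocol 6.6 the arm means "will be compared in a two-sided, two-sample t-test". SAP 2.4.2 (Primary Endpoint) makes the comparison "using a two-sided, two-sample t-test (or Wilcoxon Rank sum test as appropriate". Neither includes a covariate.

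SAP 2.1.3 makes the choice of test depend on the data: "The normality of quantitative data will be tested using the Shapiro-Wilk test". A p-value above 0.05 leads to Student's test, otherwise to the rank-sum test. The interval follows: "If assumptions of normality are violated, the 95% confidence interval will be calculated using the Hodges-Lehmann estimate". That SAP sentence comes after one about intervals within each arm. Protocol 6.6 states the same switch for the between-group interval, without naming a normality test. Neither document says whether normality is tested on pooled data or in each arm.

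For baseline, SAP 2.4.2 (Baseline Patients' Characteristics) says "Those baseline parameters will be compared in order to identify any imbalance following randomization". Its resting-echo items are heart rate, "Systolic and Diastolic blood pressures (mmHg), MR Grade, LVEF (%), LVEDD (mm) or LVEDD/BSA"; regurgitant volume is not listed. Adjustment for baseline appears only in SAP 2.4.6, as a supportive line that names neither covariate nor model. The supportive mixed model in SAP 2.1.3 has treatment, time, site and a treatment-by-site term, but no baseline term. Arm means are tabulated in any case (SAP 2.1.2 and 4.1.1).

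**The concern.** The plan needs only 19 evaluable controls, and about 21 remain after the allowed 30% loss (120 × 0.7 = 84, split 63:21). With so few, a chance difference in baseline regurgitant volume can be several millilitres, and the planned analysis neither corrects for it nor tabulates it. The core lab already measures the baseline value, so adjustment needs no new data.

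The second issue is what the primary result measures. If the pre-test fires, the formal test and interval no longer address the mean difference on which the trial was sized. Two analysts could also reach different primary results from the same data, one testing normality on pooled data and the other in each arm.

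**Working it through.** **1. The plan's own figure.** Inputs from Protocol 6.6 and SAP 2.2: difference 10 ml, SD of change 13 ml in both arms, two-sided 0.05, 3:1, Student's t-test. At 57:19, √(1/57 + 1/19) = 0.265 and the noncentrality is 10/(13 × 0.265) = 2.90 on 74 df. Power is 81.8%. At 54:18 it is 79.6%, so 76 is the smallest 3:1 total that reaches 80%. At 63:21 power is 85.5%.

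**2. Bracketing the correlation.** The baseline-to-12-month correlation ρ is not in the documents. With equal SDs at both visits, 13² = 2·SD²·(1 − ρ), so ρ = 1 − 169/(2·SD²). Protocol 6.6 gives regurgitant-volume SDs for a CRT-candidate cohort: "CRT decreased the regurgitant volume from 36 ± 19 ml to 25 ± 11 ml", and 12 ml during exercise. Applying them here is an assumption. Only the 19 ml value was measured before treatment.

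**3. Effect of adjustment.** With a common slope the residual SD is 13·√((1 + ρ)/2). Power is from 20,000 simulated trials per case, using HC3 standard errors and n − 3 df:

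| SD (ml) | ρ | Residual SD (ml) | Power 57:19 | Power 63:21 | Mean CI width 57:19 (ml) |
|---|---|---|---|---|---|
| Unadjusted t-test | – | 13.0 | 82% | 85% | 13.7 |
| 11 | 0.30 | 10.5 | 93% | 95% | 11.4 |
| 12 | 0.41 | 10.9 | 91% | 94% | 11.9 |
| 19 | 0.77 | 12.2 | 84% | 88% | 13.3 |
| 29 | 0.90 | 12.7 | 81% | 85% | no gain |

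If the SD instead fell from 19 to 11 ml, as in the cited cohort, ρ = (361 + 121 − 169)/(2 × 19 × 11) = 0.75. The residual SD is 11·√(1 − 0.75²) = 7.3 ml and power exceeds 99%.

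**4. Chance imbalance.** One standard error of the baseline difference at 57:19 is SD × 0.265: 2.9 ml (SD 11) to 5.0 ml (SD 19). It moves the unadjusted difference by (1 − ρ) times that, 2.0 to 1.2 ml of the planned 10 ml.

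**5. Where the gain disappears.** With unequal slopes at 3:1, additive ANCOVA weights the arm slopes 0.75:0.25 towards Treatment, while the most precise slope uses the reverse weights. Suppose the effect is purely proportional, with mean baseline B. The arm slopes are then 1 − 12.4/B and 1 − 2.4/B.
- ANCOVA uses 1 − 9.9/B (0.75 × 12.4 + 0.25 × 2.4 = 9.9).
- The most precise slope is 1 − 4.9/B (0.25 × 12.4 + 0.75 × 2.4 = 4.9).
- The change score uses slope 1.

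The distances from the best slope are 5.0/B and 4.9/B, so the variance ratio is about 1.00 (simulated 1.02 to 1.03 at B = 31 ml). With slopes of 0.5 (Treatment) and 1.0 (Control), ANCOVA is less precise, with variance ratio 1.06 to 1.18.

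**6. The normality switch** (simulated at 57:19, true difference −10 ml):

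| Data | Fires, pooled | Fires, either arm | Hodges-Lehmann | Mean |
|---|---|---|---|---|
| Normal | 5% | 10% | −10.0 | −10.0 |
| 15% non-implant mixture (Protocol 6.6) | 5% | 10% | −10.0 | −9.9 |
| t, 5 df (assumed) | 40% | 50% | −10.0 | −10.0 |
| Skewness −1 (assumed) | 64% | 82% | −9.9 | −10.0 |

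Two-stage type I error is 4.8 to 5.3% under the normal, t and skewed shapes. The two estimates separate when benefit is uneven. Suppose one third of treated patients improve by 30 ml and the rest not at all, so the true mean difference is −10. Hodges-Lehmann then averages −9.1 with within-group SD 13 ml. With SD 8 ml it averages −7.4; testing normality in each arm, the switch fires in 92% of trials and power falls from 79% (t-test) to 60%. These responder patterns are assumptions.

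**7. Robustness.** The HC3 model held type I error at 4.6 to 5.3% under common slopes, unequal slopes, heavy tails and skewed data, and at 4.1 to 4.7% with site effects omitted. Student's test at 57:19 gives roughly 8% if the control SD is 16 ml and 11% if it is 19.5 ml, against 13 ml in Treatment.

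**The case against.** The strongest reply is that nothing is wrong: test, parameter and sample size agree, and 84 evaluable patients already give more than the target power. The 93% and 91% figures rest on a post-CRT SD and an exercise SD. The one pre-treatment SD, 19 ml, gives only 84% against 82%. Protocol 1.3.6.2 reports earlier device effects as percentage reductions, so a proportional effect, with no gain, is plausible. The switch makes almost no difference under the non-implant mixture that the protocol itself assumes. SAP 2.4.6 could be clarified in one line without touching the primary test. Protocol 4.3 also allows each patient's assignment to be opened after that patient's own 12-month visit, so it may be too late to change the primary analysis.

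Much of this stands. The sample size is not in error, the gain depends on an unknown correlation, and the numerical effect of the switch is usually small. But a small gain is not the general case: the cited fall from 19 to 11 ml gives a large one. A supportive line without covariate or model fixes nothing in advance. A parameter stated as a mean should not depend on a pre-test. On timing, the documents do not show whether assignments have been opened for analysis, so the recommendation needs a fallback.

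**Conclusion.** The concern holds as an improvement the sponsor should make; it does not invalidate the planned test. With a common slope, equal SDs at both visits and a baseline SD of 11 to 19 ml, adjustment raises power at 57:19 from 82% to between 84 and 93% and shortens the interval from 13.7 ml to between 11.4 and 13.3 ml. There is no gain at a correlation near 0.9 or with a purely proportional effect, and some loss with strongly unequal slopes. The switch is mainly a problem of what is estimated; type I error is not materially inflated in the shapes tried. Calling the t-test valid relies on the plan's equal SDs. Confidence in the size of the gain is medium, because the correlation, the baseline SD and the non-normal shapes are all assumed.

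**What to change.** - **Primary analysis:** one linear model of change in core-lab regurgitant volume on treatment and baseline core-lab regurgitant volume, with HC3 standard errors and n − 3 degrees of freedom. Using the 12-month value as the outcome gives the same treatment estimate. Report the adjusted mean difference and 95% interval whatever a normality test shows.
- **Baseline value:** keep the SAP's existing rule: "If 2 Screening/Baseline visits are performed for a patient the latest Screening/Baseline data will be considered for analyses". State what happens when baseline is missing; SAP 2.1.1 gives no rule. Add baseline regurgitant volume to the baseline table.
- **Sensitivity analyses:** always report the unadjusted t-test and the rank-sum/Hodges-Lehmann analysis. Fit site as a random intercept in a separate sensitivity model, not in the primary.
- **Timing:** sign the change before assignments are opened for analysis (SAP 1.3.5). If they are already open, keep the t-test as primary and add this model as a named sensitivity analysis.

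The cost is one degree of freedom, an SAP revision and an amendment to Protocol 6.6 under Protocol 7.5 (Executive Committee review, justification, and ethics and regulatory submission). There is also the possible loss of precision under strongly unequal slopes. No new data or patients are needed.

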### 2.4.3. Secondary Endpoints

The secondary analysis will be performed on the ITT population. Secondary endpoints analyses will also be also performed on As-treated and Per-protocol populations as additional subgroup analyses. The secondary endpoints are to determine the procedural safety of the device and the effect of the CMCS on hemodynamics, subject function and long-term safety.

#### 2.4.3.1. Safety

The following secondary safety endpoints will measure the effect of the CMCS on safety parameters of interest, relative to the Control group.

- The rate of major adverse events, through 1 month (+7 days) and 12 months (+30 days) of follow-up.

Major Adverse Events are defined as one of the following:

- Death;
- Myocardial Infarction;
- Device Embolization;
- Vessel Erosion, requiring percutaneous or surgical intervention;
- Cardiac Perforation, requiring percutaneous or surgical intervention;
- Occurrence of cardiac surgery or percutaneous coronary intervention associated with device failure.
- The HF-hospitalizations from the time of the index procedure through 12 months (+30 days) of follow-up:
  - Rate of HF-hospitalizations;
  - Number of admissions;
  - Total associated days in the hospital.

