### 2.3. Analysis Sets

#### 2.3.1. Databases

Core laboratory Excel databases will be used to analyze hemodynamic and echocardiographic assessments.

The CEC will be responsible for adjudicating complications reported during the study that are related to study endpoints (objectives), the procedure or the device. The CEC AE review Excel database will be used to analyze safety endpoints (MAE and HF-hospitalizations).

All other analysis will be done on the e-CRF clinical database.

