## 2.4. Statistical Analyses

### 2.4.1. Patient Disposition and Follow-up

#### 2.4.1.1. Patient Populations, follow-ups and withdrawals

The number of patients present at each visit, as well as the reasons for study exit will be presented by population and treatment group as appropriate.

The corresponding average time of patients' follow-up will also be presented by population and treatment group as appropriate.

The repartition by site will also be presented.

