### 2.4.4. Safety

The following secondary safety endpoints will be performed on the ITT population and compared between the treatment and control groups:

- Incidence of adverse events (AE) and the corresponding number and percentage of patient
- Incidence of serious adverse events (SAE) and the corresponding number and percentage of patient
- Incidence of device related adverse events (ADE) and the corresponding number and percentage of patient (based on CEC adjudication)
- Incidence of procedure related adverse events and the corresponding number and percentage of patient (based on CEC adjudication)
- Incidence of device related serious adverse events (SADE) and the corresponding number and percentage of patient (based on CEC adjudication)
- Incidence of unanticipated serious adverse device effects (USADE) and the corresponding number and percentage of patient (based on CEC adjudication)
- Incidence of anticipated device effects (AADE) and the corresponding number and percentage of patient (based on CEC adjudication)

- Event Severity
- Incidence of device deficiencies and the corresponding number and percentage of patient

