### 2.4.5. Observational Data

The following analysis will be performed on the ITT population.

- Long-term safety (through 6 months (+14 days) and 12 months (+30 days) of follow-up):
  - Mortality;
  - Serious adverse events (SAE).
    - NYHA classification at each visit
    - Left ventricular hemodynamics:
      - Left ventricular end diastolic (LVEDD) and systolic (LVESD) dimensions;
      - Ejection fraction (LVEF);
      - Forward cardiac output (CO).
    - Functional Mitral Regurgitation (FMR) echocardiographic assessments
      - Vena Contracta (VC)
      - Effective regurgitant orifice area (EROA)
      - Mitral regurgitation jet area / Left atrial area (MRJA/LAA)
      - Mitral regurgitation grade
        - Left atrial size
        - Mitral annular diameter and area
        - Diuretic dose change from baseline to 6 months of follow-up and to 12 months of follow-up
        - Pulmonary artery systolic pressure (echo derived at rest & during exercise)
        - NT-BNP
        - Kansas City Cardiomyopathy Questionnaire (KCCQ)
        - Quality-of-Life Assessment (SF-12)

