## 4.3. Other types

### 4.3.1. Type 6: AE/medications

AE/Med/Deviation	Population (N=XX)			Group 1 (*) (N=XX)			Group 2 (*) (N=XX)		
	YYY (1)	n (2)	% (3)	YYY (1)	n (2)	% (3)	YYY (1)	n (2)	% (3)
At least one (*)	XX	XX	XX.X	XX	XX	XX	XX.X	XX	XX
AE/Med/Dev description 1	XX	XX	XX.X	XX	XX	XX	XX.X	XX	XX
AE/Med/Dev description 2	XX	XX	XX.X	XX	XX	XX	XX.X	XX	XX
AE/Med/Dev description 3	XX	XX	XX.X	XX	XX	XX	XX.X	XX	XX

YYY=NAE/Nmed

(1): Number of adverse events/medication of a given type

(2): Number of patients with at least one adverse event/medication of a given type

(3):  $(n / N) * 100$  (N : total number of patients)

\* if needed

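### The 12-month MAE, HF-hospitalization and mortality analyses use no individual follow-up time, and the percentage denominator is not fixed, so early exit or death misstates the results

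*SAP*

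**What the plan says.** SAP 2.4.3.1 sets two secondary safety endpoints relative to Control. One is "The rate of major adverse events, through 1 month (+7 days) and 12 months (+30 days) of follow-up". The other is "The HF-hospitalizations from the time of the index procedure through 12 months (+30 days) of follow-up", split into a rate, a number of admissions and total days in hospital. SAP 2.4.5 adds, as observational data, "Long-term safety (through 6 months (+14 days) and 12 months (+30 days) of follow-up", covering mortality and SAEs. None of these entries names an estimator, a denominator, a censoring rule or a treatment of death.

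The general methods are in SAP 2.1.2 and 2.1.3. Continuous data go to Student or Wilcoxon. For categorical data, "the appropriate test will be chosen depending on the expected cell frequencies", the choice being Chi-square or Fisher. On denominators, SAP 2.1.2 bases percentages on non-missing observations. The adverse-event layout in SAP 4.3.1 instead divides by N, defined as "N : total number of patients".

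The nearest convention for safety outcomes is the adverse-event one. SAP 2.4.4 uses entries such as "Incidence of serious adverse events (SAE) and the corresponding number and percentage of patient", and SAP 2.3.1 says "The CEC AE review Excel database will be used to analyze safety endpoints (MAE and HF-hospitalizations". Follow-up time appears only in the disposition section (SAP 2.4.1.1: "The corresponding average time of patients" and so on, by population and group). Protocol 6.8 makes secondary and observational results descriptive and supportive. SAP 2.2 and Protocol 6.7 plan for about 30% attrition over 12 months, combining deaths, missing data and losses.

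**The concern.** Protocol 3.8.6.1 allows early exit for loss to follow-up, withdrawn consent, transplantation or another confounding intervention, and physician discretion. Patients will therefore be observed for different lengths of time.

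A simple percentage must then treat a patient who leaves event-free at, say, month 4 in one of two ways. Kept in the denominator, the patient counts as event-free to month 12 and the risk is too low. Dropped as missing, the patient's event-free months are lost and the risk is too high. The SAP's two rules point in opposite directions and neither is tied to MAE or mortality, so the choice falls to whoever programs the table.

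Admissions and hospital days are exposed in a second way. Counting stops at death as well as at exit, so an arm with more early deaths shows fewer admissions at the same true rate. At stake are the trial's two secondary safety endpoints at 12 months and the observational mortality comparison.

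**Working it through.** **The plan's own figures.** The documents state no event rate, power or sample size for MAE, mortality or HF hospitalization. The stated sample size is for regurgitant volume and reproduces: with a difference of 10 ml, SD 13 ml, 3:1 allocation and two-sided 0.05, the noncentral t gives power 0.796 at 54 + 18 = 72 and 0.8175 at 57 + 19 = 76. With 120 randomized, 30% loss leaves 120 × 0.70 = 84, above 76. Nothing below changes this.

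**Assumptions.** True 12-month MAE risk p is taken as 10%, 20% or 30%. Exit without an event by 12 months, c, is taken as 5% to 30%. Hazards are constant and exit is independent of events: h = −ln(1 − p), g = −ln(1 − c). Death is itself an MAE, so only exits censor MAE.

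**MAE, all patients in the denominator.** Expected percentage = h/(h + g) × [1 − (1 − p)(1 − c)]. For p = 0.20, h = 0.2231:
- c = 0.10: 0.2231/0.3285 × 0.28 = 0.1902
- c = 0.20: 0.5 × 0.36 = 0.1800
- c = 0.30: 0.2231/0.5798 × 0.44 = 0.1693

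**MAE, non-missing denominator**, taking event-free early exits as missing. Expected percentage = events/(events + event-free completers):
- c = 0.10: 0.1902/(0.1902 + 0.72) = 0.2090
- c = 0.20: 0.1800/(0.1800 + 0.64) = 0.2195
- c = 0.30: 0.1693/(0.1693 + 0.56) = 0.2322

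At 30% exit the same data read 16.9% or 23.2%, a spread of 6.3 points. At 5% exit they read 19.5% or 20.4%. At 30% exit, a true 10% reads 8.4% or 11.8%, and a true 30% reads 25.5% or 34.2%. Kaplan-Meier targets p in every case.

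**Is 30% realistic?** It is a ceiling, since the planned attrition includes deaths and missing echo data. If 10 of the 30 points were deaths and all the rest safety exits, c = 1 − 0.70/0.90 = 0.222, and the all-patients figure is 17.8%.

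**Admissions and days.** If a fraction a dies or exits at a constant hazard, mean time observed is a/(−ln(1 − a)) years: 0.949, 0.896 and 0.841 for a = 10%, 20% and 30%. Unadjusted totals fall short by 5%, 10% and 16%.

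**Between arms, equal true rates.**
- Equal loss: ratio 1.00 for both MAE and admissions.
- 20% vs 10% lost: admissions ratio 0.896/0.949 = 0.94. Mortality of 20% vs 10% with no other loss gives the same 0.94.
- 30% vs 10% lost: admissions ratio 0.841/0.949 = 0.89.
- MAE difference on all patients at p = 0.20: 18.0 − 19.0 = −1.0 point (20% vs 10% exit) and 16.9 − 19.0 = −2.1 points (30% vs 10%). On the non-missing rule the sign flips: 23.2 − 20.9 = +2.3 points for 30% vs 10%.

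**Scale.** With 90 and 30 patients at 20% risk, the 95% half-width of the difference is 1.96 × √(0.2 × 0.8 × (1/90 + 1/30)) = 0.165, or 16.5 points.

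**1-month MAE.** With g = −ln(0.7)/12 for one month, a true 2.0% shows as 1.97%. A simple proportion is adequate there.

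**The case against.** The strongest reply is that these endpoints are unpowered, descriptive and supportive, that follow-up and exit reasons are already tabulated by group, and that the distortion is small beside a 16.5-point half-width. At 5% to 10% exit, a true 20% shows as 19.5% to 19.0% on all patients. All of that stands and limits the weight of the point. It does not make the estimates well defined.

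It may also be said that the absence of time-based methods is inferred from silence. SAP 2.4.3.1 lists a hospitalization rate separately from a count of admissions, so a person-time rate is not excluded. The SAP contents list a survival-analysis layout, but its bookmark is broken and the body holds no such layout or method. LOCF (SAP 2.1.1) does not help: carrying no event forward repeats the all-patients calculation.

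Four stronger readings are tempting, and the documents do not support them:
- *That reported risk will be too low in both arms.* This needs the all-patients rule. The non-missing rule reverses the sign, and neither is assigned to these endpoints.
- *That the treatment comparison is biased.* This needs unequal loss or death, which is not shown. The Treatment-only patients who exit at 1 month without an implant attempt are outside the SAP's ITT set (2.3.2), although Protocol 6.2 would keep them.
- *That cross-over or the +30-day window leaves a large uncounted period.* Protocol 5.1 and 5.1.2 record events through the final scheduled visit, and Protocol 3.8.7 allows cross-over only after 1-year follow-up is complete.
- *That mortality is a secondary endpoint left unprotected.* It is observational (SAP 2.4.5), and Protocol 3.8.6.3 seeks survival data to 1 year after consent is withdrawn.

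**Conclusion.** The point holds and is worth correcting. As written, no stated analysis of 12-month MAE, HF hospitalization or mortality uses individual follow-up time, and the SAP contains two conflicting denominator rules. Early exit therefore misstates 12-month risk, in a direction that depends on the rule applied. At a true 20% risk the error runs from about 1 point at 10% exit to about 3 points at 30%. Unadjusted admissions and days fall short by about 5% to 16% at 10% to 30% loss.

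These sizes rest on assumed event and exit rates, constant hazards and independent exit, and the upper end is a ceiling. They concern absolute estimates within each arm; any distortion between arms is conditional on unequal loss or death. The primary endpoint, the sample size and, for practical purposes, 1-month MAE are not affected.

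**What to change.** Amend SAP 2.4.3.1 and 2.4.5 as follows.

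1. Estimate 12-month MAE and mortality by Kaplan-Meier, with a 95% confidence interval for the between-group difference. Censor at last contact (last survival contact for mortality) or the 12-month visit, consistent with Protocol 5.1 and 5.1.2. Keep a simple proportion for 1-month MAE.
2. Analyse HF admissions with a count model, for example negative binomial, with log follow-up time as offset. Report hospital days per patient-year.
3. Report deaths by arm beside the admissions results, and add a sensitivity analysis that treats death as a terminal event. The offset alone does not deal with death when it is related to the admission rate.
4. Use all ITT patients as the denominator for any crude percentage of these outcomes, and say that this overrides the non-missing rule in SAP 2.1.2.
5. State that censoring is assumed non-informative, and read the results with the exit-reason table already planned in SAP 2.4.1.1. Withdrawal for transplantation is the clearest threat to that assumption.

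The cost is SAP wording and standard programming. Event onset dates are already collected (Protocol 5.1.2), and length of stay already runs from admission to discharge (Protocol 9.2). The downsides are slightly more complex tables and the censoring assumption itself.
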